### 3.3. Sample size

The trial's revised target enrollment is 455 participants, which will be sufficient to detect an increase in the proportion of patients who are symptom free 50% to 65% (15 percentage point increase) at 14 days from enrollment.

With 455 participants, the trial will have 80% power to detect an increase of 15 percentage points in the percentage of patients who are symptom free at 14-d under the following assumptions:

- 2:1 allocation ratio of azithromycin : placebo
- 50% symptom-free under placebo at the 14-day measurement (binomial outcome)
- 20% loss to follow-up
- 2-sided alpha of 0.05, power = 0.8.

- A single interim analysis with 50% of primary outcomes collected with stopping guideline determined using the Lan-DeMets spending function approach with an O'Brien and Fleming boundary.

The table below shows sample sizes under several effect size scenarios, assuming azithromycin increases the proportion of patients who are symptom free by 0.1 to 0.2 compared to placebo.

Sample size required for a fixed design allowing for 20% loss to follow-up. Calculations assume 2-sided alpha of 0.05 and 80% power.

p placebo	p azithro	RD	N placebo	N azithro	N Total
0.5	0.60	0.10	348	695	1,043
0.5	0.61	0.11	287	573	860
0.5	0.62	0.12	240	479	719
0.5	0.63	0.13	204	407	611
0.5	0.64	0.14	175	349	524
0.5	0.65	0.15	152	303	455
0.5	0.66	0.16	133	265	398
0.5	0.67	0.17	117	233	350
0.5	0.68	0.18	104	207	311
0.5	0.69	0.19	93	185	278
0.5	0.70	0.20	83	165	248

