## Analysis N Z Nominal p Spend
## 1 228 2.96 0.0015 0.0015
## 2 456 1.97 0.0245 0.0235
## Total 0.0250
##

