## 6. Analysis

### 6.1. Outcome definitions

#### Primary Outcome:

The primary outcome will be free of symptoms at 14 days after the electronic enrollment assessment. Symptoms include: cough, fever, myalgia, anosmia, shortness of breath (and related abilities such as ability to walk across a room or up a flight of stairs), fatigue, conjunctivitis, and orthostatic symptoms.

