## **6.3. Missing data**

If outcome data are missing for >15% of participants we will report results from sensitivity analyses for missing data [4,5]. We selected 15% missing because trials with >20% missing values are thought to be a concern for bias [6]. The primary analysis will account for censoring but will assume outcomes are missing completely at random. We will relax this assumption slightly, assuming that outcomes are missing at random (MAR) with an inverse-probability weighted (IPW) estimator using cumulative incidence through 14 days as the binary endpoint. We will model the probability of censoring as a function of baseline patient characteristics with a logistic regression model, and will use the inverse of the predicted probabilities from the model to re-weight the analysis population to reflect the full study population at the time of enrollment, using a doubly-robust targeted maximum likelihood estimator that also includes an outcome model using the same covariates [7]. Baseline characteristics used in the censoring model will include age, sex, race/ethnicity, zip code, comorbidities, concomitant medications, symptoms at enrollment, insurance status, alcohol use, tobacco/e-cigarette/marijuana use, and household composition. We will additionally consider a range of scenarios assuming the outcomes are missing not at random (MNAR), *i.e.* systematically, using a pattern mixture model approach described by Little et al. [4], whereby we model cumulative incidence through 14 days with a linear probability model as a function of covariates listed for the IPW estimator; missing outcomes will then be imputed using the model fit to predict, adding a shift parameter  $\Delta$  that we vary across a range of values.

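### SAP 6.3 gives its missing-not-at-random analysis one shift with no arm index or values; read as a common shift, it leaves the risk difference almost unmoved when dropout is similar in the two arms

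*SAP*

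**What the plan says.** SAP 6.3 sets the trigger: "If outcome data are missing for >15% of participants we will report results from sensitivity analyses for missing data". Two sensitivity analyses follow.

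- **Missing at random.** An inverse-probability-weighted, targeted maximum likelihood estimator "using cumulative incidence through 14 days as the binary endpoint". The censoring covariates are a list of baseline characteristics, and the outcome model uses the same list. Treatment arm is not named.
- **Missing not at random.** "We will additionally consider a range of scenarios assuming the outcomes are missing not at random (MNAR"), by a pattern-mixture approach taken from a cited source. In it, "we model cumulative incidence through 14 days with a linear probability model as a function of covariates listed for the IPW estimator", and "missing outcomes will then be imputed using the model fit to predict, adding a shift parameter" that is varied over a range. No limits, step, direction, arm index or tipping-point rule is given.

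The primary outcome has changed: "The primary outcome will be free of symptoms at 14 days after the electronic enrollment assessment" (SAP 6.1). SAP 6.2 compares the arms by the risk difference. The superseded version 5 in the SAP appendix has the same sensitivity-analysis wording, written when the primary outcome was hospitalization or death. Protocol section 9 refers to the SAP and adds nothing on missing data.

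**The concern.** The departure most able to create or hide a treatment effect is one that differs between arms, for example azithromycin participants who still have symptoms being less likely to return the Day 14 questionnaire. A single shift applied to both arms does not represent that. When dropout is similar, it moves both proportions by the same amount and cancels from the risk difference. A flat line over all shifts could be reported as robustness when the assumption that matters was never varied.

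The analysis may well be needed. The sample size allows for "20% loss to follow-up" (SAP 3.3), above the 15% trigger. Day 14 symptoms are self-reported remotely, and the next-of-kin contact in Protocol 5.7 seeks vital status and hospitalization, not symptoms.

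The carried-over endpoint adds ambiguity. For hospitalization or death, a positive shift was the unfavourable direction; for symptom-free status it is the favourable one. The SAP states no sign convention.

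**Working it through.** **Inputs.** From SAP 3.3: 2:1 allocation, 303 azithromycin and 152 placebo, symptom-free 65% v 50%, 20% loss overall. From the final row of the efficacy-bound table in SAP 3.5 ("2 456 1.97 0.0245 0.0235"): Z = 1.97, one-sided p 0.0245. The documents give no dropout by arm; every by-arm figure and every shift value below is an assumption.

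**The plan's own N.** With pooled proportion 0.60, placebo n = [1.960 × √(0.24 × 1.5) + 0.842 × √(0.25 + 0.2275/2)]² / 0.15² = 125.97. Multiplying by 1.2 gives 152, and twice the unrounded n times 1.2 gives 303; the total is 455, as stated. A factor of 1.2 corresponds to 1 − 1/1.2 = 16.7% loss, still above the 15% trigger.

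**Formula.** Let mA and mP be the missing fractions and ΔA and ΔP the shifts. With arm in the model, the completed proportion in each arm is p_obs + m × Δ, so

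RD = RD_obs + mA × ΔA − mP × ΔP.

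A common Δ adds Δ × (mA − mP).

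**Common shift, observed RD 15 points:**

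| Missing, azithromycin / placebo | Δ = −0.3 | Δ = 0 | Δ = +0.3 |
|---|---|---|---|
| 20% / 20% | 15.0 | 15.0 | 15.0 |
| 22% / 18% | 13.8 | 15.0 | 16.2 |
| 15% / 25% | 18.0 | 15.0 | 12.0 |
| 25% / 15% | 12.0 | 15.0 | 18.0 |

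The imbalance fixes the sign and size of the slope.

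**Separate shifts, 20% / 20%:**

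- −0.3 in azithromycin only: 15 − 6 = 9 points.
- −0.3 in placebo only: 15 + 6 = 21 points.
- −0.3 in azithromycin with +0.3 in placebo: 15 − 6 − 6 = 3 points. The reverse gives 27.

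**Tipping point.** At 20% / 20%, SE = √(0.65 × 0.35/242.4 + 0.25/121.6) = 0.0547, so significance needs RD = 1.97 × 0.0547 = 0.1078.

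- Azithromycin only: (0.1078 − 0.15)/0.20 = −0.21.
- Equal and opposite shifts: (0.1078 − 0.15)/0.40 = −0.11 in azithromycin with +0.11 in placebo.
- Azithromycin only, other cases: −0.11 if the observed RD is 13 points and −0.31 if it is 17; −0.30 at 15% missing and −0.15 at 25% missing, with RD 15.

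These are Wald approximations using the observed-case SE, not the planned permutation test. A multiple-imputation simulation (30 imputations, 1,500 replicates) agrees: mean Z is 2.74 at no shift, 1.99 at −0.20 and 1.82 at −0.25.

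**A misleading flat result.** Suppose there is no true effect (50% v 50%). Azithromycin loses 30% of symptomatic and 10% of symptom-free participants; placebo loses 20% at random. Observed azithromycin is 0.45/(0.45 + 0.35) = 56.25%, so the complete-case RD is 6.25 points. By the formula, a common shift leaves it there at every value. The missing azithromycin participants are really 0.05/0.20 = 25% symptom-free, a departure of −0.3125. Applied to azithromycin only, that gives 6.25 − 0.20 × 31.25 = 0.

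**Arm left out of the model, 20% / 20%.** Both arms receive the same imputed mean, so RD = 0.8 × 15 = 12 points at every common shift.

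**The case against.** The strongest reply is that this is silence, not a wrong choice. The SAP never says that the shift is common. It promises several scenarios and cites a method that may allow arm-specific shifts; the source is not available here. That stands, so the point is under-specification. A reader might infer that the plan commits to a common shift, or that it excludes arm from the model. The text supports neither: the covariate list omits arm without forbidding it, and a targeted estimator of a treatment contrast would normally contain it.

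Four further limits also stand.

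- With unequal dropout, a two-sided common range moves the RD both ways: 6 points in total at a 10-point imbalance. It is not empty.
- Exact flatness needs unbounded imputations. With a covariate that moves risk by ±0.1, a shift of +0.3 puts half of the azithromycin imputations at 1.05. Capping them at 1 costs 0.20 × 0.5 × 0.05 = 0.005, so the RD is about 14.5 points.
- Flatness applies to the RD. The prevalence ratio, also to be reported, goes from 0.59/0.44 = 1.34 to 0.71/0.56 = 1.27 as a common shift goes from −0.3 to +0.3.
- Withdrawals are reported by arm with reasons (SAP 5.4) and treatment is masked, so some evidence on differential dropout will exist. Neither tests its effect on the RD.

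The old endpoint wording still suits hospitalization or death by 14 days, now a secondary outcome, and a two-sided range covers both signs. The labelling problem is therefore a clarification, not an error in a result.

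**Conclusion.** The concern holds as under-specification of a sensitivity analysis. On the most literal reading, the RD stays at 15 points over all common shifts at equal dropout, apart from small capping effects, while about −0.21 in azithromycin only would remove significance. If arm were omitted from the model, the RD would be about 12 points.

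These sizes assume 20% missing in each arm and observed rates of 65% v 50%. The tipping point depends on both, and the 3-to-27-point span reflects the illustrative ±0.3 grid.

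A reader might also infer that the primary result is at risk. It is not: the primary permutation test does not use this analysis, which is reported only above 15% missing. The 20% loss figure makes that likely but is a planning allowance, not a forecast. The change should still be made, because the arm structure and range are otherwise open to choice after the data are seen.

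**What to change.** In SAP 6.3:

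- (a) Use separate shifts for azithromycin and placebo over a stated two-way grid that includes opposite directions (for illustration, −0.3 to +0.3 in each arm), and report the tipping point.
- (b) State that arm is in the imputation and outcome models, or fit them by arm.
- (c) For the primary outcome, replace the cumulative-incidence endpoint with symptom-free at Day 14 in both the missing-at-random and missing-not-at-random text, and state that a negative shift means fewer missing participants are symptom-free.

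The cost is a few SAP phrases and a little more code and reporting. No new data are needed and the primary analysis does not change.

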## **6.4. Additional analyses**

### **Pre-specified Subgroup Analyses**

In secondary analyses, we will estimate differences separately by the following subgroups:

- Age >60 versus ≤ 60
- “High risk” versus low risk patients, with “high risk” defined as Age >60 and reported hypertension, cardiovascular disease, diabetes, or obstructive or restrictive lung disease at enrollment.
- Presence of COVID-19 symptoms at enrollment versus asymptomatic at enrollment.

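### The three subgroup factors are analysed level by level with no comparison between levels, so chance differences can readily be read as differing effects

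*SAP*

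**What the plan says.** SAP 6.4 (Additional analyses) places the subgroups among the secondary analyses and gives the method in one clause: "we will estimate differences separately by the following subgroups". The three factors are age above 60 versus 60 or below, high versus low risk, and symptomatic versus asymptomatic at enrollment. High risk is "defined as Age >60 and reported hypertension, cardiovascular disease, diabetes, or obstructive or restrictive lung disease at enrollment", so as written it lies wholly inside the older age group.

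Nothing else in the current documents adds a comparison between levels. Protocol section 9 describes a model whose only covariate is treatment arm. SAP 6.2 says that significance for primary and secondary analyses follows the final alpha-spending function, and does not mention subgroups. Protocol 15.4 includes subgroup analyses in the DSMC Closed Reports. SAP version 5, kept in the SAP appendix, has the same subgroup wording.

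**The concern.** Whether an effect differs between two groups is a question about the difference between the two estimates. Two separate estimates, each with its own interval or P-value, do not answer it. One level can be significant and the other not because the levels differ in size or by chance, even when the true effect is the same in both.

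At stake is a false statement about who benefits, for example that the drug works in younger but not older patients. SAP 6.4 calls the subgroups secondary, and SAP 6.2 applies the final threshold to secondary analyses. A reader could therefore reasonably judge each level against that threshold, and nothing in the plan warns against it.

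**Working it through.** **Inputs.** From SAP 3.3: "revised target enrollment is 455 participants"; "2:1 allocation ratio of azithromycin : placebo"; "20% loss to follow-up"; "2-sided alpha of 0.05, power = 0.8"; 50% symptom free on placebo and 65% on azithromycin. From SAP 3.5: final nominal one-sided P of 0.0245, that is 2 × 0.0245 = 0.049 two-sided (z = 1.969), which is also the level in Protocol 3.5. Subgroup sizes are not given, so a smaller level of 10% to 50% is assumed.

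**The plan's own figure.** For two proportions at 2:1 with pooled variance, the pooled rate is (0.50 + 2 × 0.65)/3 = 0.60, and placebo n = [1.960 × √(0.60 × 0.40 × 1.5) + 0.842 × √(0.25 + 0.2275/2)]² / 0.15² = 125.97. Multiplying by 1.20 gives 151.2 → 152 placebo and 302.3 → 303 azithromycin, total 455. The SAP figure reproduces. Evaluable after 20% loss: 455 × 0.80 = 364, with overall power of 78.5% at 0.05.

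**Separate reading when the effect is uniform.** In a level with n evaluable at 2:1, SE(RD) = √[0.25/(n/3) + 0.2275/(2n/3)] = √(1.09125/n). Power in that level is Φ(0.15/SE − 1.969). With powers a and b in the two levels, the chance that exactly one is significant is a(1 − b) + b(1 − a).

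For 20:80, n = 72.8 and 291.2; SE = 0.1224 and 0.0612; a = Φ(−0.744) = 0.229 and b = Φ(0.482) = 0.685; 0.229 × 0.315 + 0.685 × 0.771 = 0.60. The difference between the two estimates has SE √(0.1224² + 0.0612²) = 0.137.

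| Split | Power, smaller / larger level | Exactly one significant | 95% chance range of the difference between levels | Chance of a gap of 15 points or more |
|---|---|---|---|---|
| 50:50 | 49% / 49% | 50% | ±21 points | 17% |
| 30:70 | 32% / 63% | 55% | ±23 points | 21% |
| 20:80 | 23% / 69% | 60% | ±27 points | 27% |
| 10:90 | 14% / 74% | 67% | ±36 points | 41% |

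**All three factors together.** These results come from 20,000 simulated trials per setting with 364 evaluable. The assumptions are age above 60 in 20% to 40%, a listed comorbidity in 60% of those, and symptoms at enrollment in 80% to 90%.

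- Uniform 15-point effect: at least one factor shows a significant/non-significant split in about 80% to 84% of trials.
- No effect: at least one of the six level results is significant in about 19% to 20%.
- Interaction tests instead (Wald, three factors): at least one is significant in about 14% to 17% of trials in either scenario. Three independent tests at 0.05 would give 1 − 0.95³ = 14.3%.

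**Power of the interaction test.** For a true 15-point difference between subgroup effects at 0.05, power is 28% (50:50), 24% (30:70), 20% (20:80) and 13% (10:90). The difference detectable with 80% power is 2.80 × SE of the difference, or 31 to 51 points.

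**The case against.** The best defence is that the SAP promises estimates and no more. It nowhere says that within-level P-values will be compared or that effect modification will be claimed. The sentence on significance in SAP 6.2 stands under the primary outcome and does not mention subgroups. This stands. The plan leaves room for a misreading but does not prescribe one, and a reader who infers that false subgroup claims will follow goes beyond the text.

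A second tempting inference is a 26% chance of at least one false positive with no effect, from 1 − 0.951⁶. That needs six independent results. Here high risk is nested in the older age group and all three factors divide the same participants, so the simulated 19% to 20% is the figure to use.

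Third, the interaction test is weak, and with no effect at all it improves little on separate reading (about 14% to 17% against 19% to 20%). This is also true. The gain lies in the uniform-effect case, where about 80% to 84% falls to about 14% to 17%. Weak tests are a reason to state that these data can seldom support subgroup claims. They are not a reason to leave the comparison out.

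Fourth, one might call the high-risk definition an error because it is nested in age and its low-risk comparator is mixed. The documents do not support that. It is a composite chosen in advance, with its overlap visible, and a further comorbidity split would only add another test.

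Finally, the subgroups are few, pre-specified and secondary, which limits the consequence.

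**Conclusion.** The point holds as a gap in the method. SAP 6.4 prescribes separate estimation, and no between-level comparison appears in either document. With a uniform 15-point effect and 364 evaluable, a factor shows significance in exactly one level with probability 50% to 67% for splits from 50:50 to 10:90. With no effect, about 19% to 20% of trials have at least one significant level result. The first range rests on the SAP's design assumptions and on assumed subgroup sizes; the second also rests on the assumed comorbidity share and on a 50% symptom-free rate in both arms.

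The primary analysis, its alpha and the sample size are untouched. The documents support saying that chance differences can readily be read as differing effects, not that they will be. This is an inexpensive improvement that should be made.

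**What to change.** In SAP 6.4, for each of the three existing factors:

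- Keep the level-specific estimates with 95% CIs, and add the difference in risk differences with its 95% CI.
- Add an interaction P-value from a risk-difference model with a treatment-by-subgroup term, using a Wald test, a bootstrap, or a permutation that preserves the overall treatment effect. Simply permuting treatment within levels is not suitable: it tests no effect in any level, not equal effects.
- State that significance within a level will not be used to claim differing effects, and that the subgroup results are exploratory.
- State the limits: about 13% to 28% power for a 15-point difference between subgroup effects, and about a 15% chance of at least one false positive over three tests. A non-significant interaction therefore does not show that effects are equal.

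No further subgroup split is needed. The cost is a few sentences and one model term per factor. No new data are required, since age, comorbidities and symptoms at enrollment are already among the baseline characteristics in SAP 6.3.

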## 6.5. Harms

Section 10 of the trial protocol includes details of adverse event monitoring and reporting. All serious adverse events including deaths will be recorded for the period between the date the first dose of azithromycin or placebo and the date of the primary endpoint, 14 days later, and through the final follow-up at 21 days.

## 6.6. Statistical software

Analyses will be conducted using R version 4.0 or later. We will strive to make all replication files publicly available along with the trial results through the Proctor Foundation’s GitHub page and other public repositories such as the Open Science Framework and Zenodo.

## 8. Revision history

Version	Date	Summary of Changes, Justification, and Timing vis-à-vis key trial events (enrollment completion, interim analyses, unmasking, etc)
1	2020-03-28	
 
• First draft
 

2	2020-03-28	
 
• Updated administrative information
 

3	2020-04-03	
 
• Provided additional detail in the interim monitoring section.
 

4	2020-05-05	
 
• Update to reflect discussions during the trial's first DSMC meeting on April 8, 2020, as well as input from the FDA through the IND approval process, including: 
 
• Add secondary outcomes beyond viral load at day 3, including analysis details for each
 
• Add pre-specified subgroup analysis (previously none)
 
• Remove the futility bound for interim analyses
 
• Update the interim analysis alpha spending function to Lan-DeMets (harmonization with other COVID-19 therapeutic trials)
 
• Update the primary analysis to be based on a Kaplan-Meier estimator rather than cumulative proportions to explicitly account for censoring.
 
• Add language regarding a possible expansion of sample size to target a smaller detectable effect (RR = 0.8 rather than RR = 0.6) if large-scale enrollment is possible.
 
• Made risk difference the primary comparison with risk ratio (RR) an additional contrast we plan to report.
 
• Include details of masked sample-size re-assessment committee, and specific timing for masked sample size re-assessment.
 
• Add details of possible sensitivity analyses for missing outcomes under MAR and MNAR
 
 
 

5	2020-05-29	
 
• Revised the interim sample size evaluation process and group who will be involved in the decision making process. (version 5 included in the Appendix)
 

6	2020-12-15	
 
• Changed the trial's primary outcome from hospitalization/death by 14-d to symptom free at 14-d
 
• Updated the sample size calculation for the new outcome, revising the trial's planned enrollment to N=455.
 
• Updated the interim analysis plan to propose a single interim efficacy analysis when 50% of participants have reached the primary endpoint.
 
• Simplified the missing data section with demotion of hospitalization/death to a secondary outcome, since the interim analyses will no longer include that outcome.
 

## 2. Introduction

### 2.1. Background and rationale

Identification of a safe, effective treatment for individuals with mild or moderate COVID-19 that prevents disease progression and reduces hospitalization would reduce the burden on the health system. High dose hydroxychloroquine is being evaluated for SARS-CoV-2 prevention and COVID-19 disease treatment, but has a high risk of a number of potentially severe adverse events. Recent evidence has indicated that the broad-spectrum macrolide azithromycin may have some activity against coronaviruses. A large community randomized trial in Niger demonstrated reduced viral load among children with commensal coronaviruses (prior to the emergence of SARS-CoV-2) in communities receiving biannual mass azithromycin distribution compared to placebo (submitted). In SARS-CoV-2 patients in France, the addition of azithromycin to a hydroxychloroquine regimen appeared to decrease SARS-CoV-2 positivity by PCR compared to hydroxychloroquine-only and control patients. Azithromycin is generally well-tolerated and may be an attractive option for treating patients with mild disease.

